#### Safety outcome analysis covariates

Variables listed below are included in multivariable analyses for primary and secondary outcomes listed above. Variables are also included in any associated subgroup, heterogeneity of treatment, and sensitivity analyses.

- Age (**age**, continuous)
- Female sex (sex, binary)
- Weighted Elixhauser comorbidity score (elixhauser\_vw, continuous)
- Insurance (insurance, categorical)
- First-available temperature in ED (vs\_temp\_cat, categorical)
- First-available systolic blood pressure in ED (**vs\_sbp**, continuous)
- Acute physiology score (aps\_24h, continuous)

**Figure 3. Adjustment variables for safety outcome multivariable analyses.** The primary exposure is arrival to the intervention ED post-intervention. White symbols indicate potential confounders or precision variables included in the multivariable model, red variables indicate potential confounders not required for the minimal adjustment set, gray symbols represent an unobserved confounder, and blue symbols (other than the outcome) represent an outcome ancestor not included in the multivariable multivariable model.

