#### Primary and secondary analyses

```
dag {
"Arrival to intervention ED post-intervention" [exposure,pos="-1.196,0.491"]
"Door-to-antibiotic time" [outcome,pos="1.007,0.477"]
"ED arrival mode" [adjusted,pos="-0.485,0.630"]
"Elixhauser score" [adjusted,pos="0.565,-0.356"]
"Illness severity" [latent,pos="-0.139,0.781"]
"Initial SBP" [adjusted, pos="-0.104, 1.525"]
"Long-term care" [adjusted,pos="-1.122,-0.086"]
"O2 sat" [pos="1.453,0.736"]
"Preferred language" [adjusted,pos="-0.378,-0.501"]
"SOFA score" [adjusted,pos="0.269,1.938"]
"Suspected infection source" [adjusted,pos="0.536,-1.411"]
APS [adjusted, pos="-0.561, 1.300"]
Age [adjusted, pos="-1.631, -0.018"]
GCS [pos="0.214,0.680"]
HR [pos="1.331,1.495"]
Lactate [pos="0.977,2.039"]
RR [pos="1.106,1.680"]
Sex [adjusted,pos="-1.399,-0.383"]
Temperature [pos="0.798,1.651"]
WBC [pos="1.406,1.039"]
"Arrival to intervention ED post-intervention" -> "Door-to-antibiotic time"
"ED arrival mode" -> "Arrival to intervention ED post-intervention"
"ED arrival mode" -> "Door-to-antibiotic time"
"Elixhauser score" -> "Arrival to intervention ED post-intervention"
"Elixhauser score" -> "Door-to-antibiotic time"
"Elixhauser score" -> "Illness severity"
"Elixhauser score" -> "Long-term care"
"Illness severity" -> "ED arrival mode"
"Illness severity" -> "Initial SBP"
"Illness severity" -> "SOFA score"
"Illness severity" -> APS
"Illness severity" -> GCS
"Initial SBP" -> "Door-to-antibiotic time"
"Initial SBP" -> "SOFA score"
```

```
"Initial SBP" -> APS
"Initial SBP" -> Lactate
"Long-term care" -> "Arrival to intervention ED post-intervention"
"Long-term care" -> "ED arrival mode"
"Long-term care" -> "Suspected infection source"
"O2 sat" -> "Door-to-antibiotic time"
"O2 sat" -> "SOFA score"
"O2 sat" -> APS
"Preferred language" -> "Arrival to intervention ED post-intervention"
"Preferred language" -> "Door-to-antibiotic time"
"Preferred language" -> "ED arrival mode"
"SOFA score" -> "Door-to-antibiotic time"
"Suspected infection source" -> "Door-to-antibiotic time"
"Suspected infection source" -> "Illness severity"
APS -> "Door-to-antibiotic time"
Age -> "Arrival to intervention ED post-intervention"
Age -> "Door-to-antibiotic time"
Age -> "ED arrival mode"
Age -> "Long-term care"
Age -> "Preferred language"
GCS -> "Door-to-antibiotic time"
GCS -> "SOFA score"
GCS -> APS
HR -> "Door-to-antibiotic time"
HR \rightarrow APS
Lactate -> "Door-to-antibiotic time"
RR -> "Door-to-antibiotic time"
RR -> APS

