#### Safety analyses

#### dag {

```
"Arrival to intervention ED post-intervention" [exposure,pos="-1.196,0.491"]
"Elixhauser score" [adjusted,pos="0.565,-0.356"]
"Illness severity" [latent,pos="-1.121,1.505"]
"Initial SBP" [adjusted, pos="-0.147, 1.833"]
"O2 sat" [pos="1.453,0.736"]
"Preferred language" [pos="-0.383,-0.972"]
"Process outcomes" [outcome,pos="1.007,0.477"]
APS [adjusted,pos="-0.561,1.300"]
Age [adjusted, pos="-1.631, -0.018"]
GCS [pos="-0.742,1.945"]
HR [pos="1.254,1.569"]
Insurance [adjusted,pos="-0.343,-0.344"]
RR [pos="0.965,1.669"]
Sex [adjusted,pos="-1.377,-0.479"]
Temperature [adjusted, pos="0.476, 1.904"]
WBC [pos="1.372,1.100"]
"Arrival to intervention ED post-intervention" -> "Process outcomes"
"Elixhauser score" -> "Arrival to intervention ED post-intervention"
"Elixhauser score" -> "Illness severity"
"Elixhauser score" -> "Process outcomes"
"Elixhauser score" -> Insurance
"Illness severity" -> "Initial SBP"
"Illness severity" -> APS
"Illness severity" -> GCS
"Initial SBP" -> "Process outcomes"
"Initial SBP" -> APS
"O2 sat" -> "Process outcomes"
"O2 sat" -> APS
"Preferred language" -> "Process outcomes"
"Preferred language" -> Insurance
APS -> "Process outcomes"
Age -> "Arrival to intervention ED post-intervention"
Age -> "Preferred language"
Age -> "Process outcomes"
Age -> Insurance
GCS -> APS
HR -> "Process outcomes"
HR -> APS
Insurance -> "Arrival to intervention ED post-intervention"
Insurance -> "Process outcomes"
RR -> "Process outcomes"
```

```
RR -> APS
Sex -> "Arrival to intervention ED post-intervention"
Sex -> "Process outcomes"
Temperature -> "Process outcomes"
WBC -> "Process outcomes"
WBC -> APS
WBC -> HR
}
```

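### The SAP's two causal graphs give the same exposure different causes, and the safety covariate set is sufficient only if the primary graph's causes are set aside

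*SAP*

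**What the plan says.** The SAP derives its covariates from two directed acyclic graphs, whose code is in its Appendix. Both use the same exposure node, arrival at the intervention ED after implementation.

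- **Primary and secondary graph.** Arrows run into the exposure from age, sex, Elixhauser score, ED arrival mode, long-term care ("Long-term care' -> 'Arrival to intervention ED post-intervention") and language ("Preferred language' -> 'Arrival to intervention ED post-intervention"). All six are in the primary and secondary covariate list.
- **Safety graph.** Arrows run into the exposure from age, sex, Elixhauser score and insurance ("Insurance -> 'Arrival to intervention ED post-intervention"). Language causes the outcome ("Preferred language' -> 'Process outcomes"; the outcome node carries that name although the graph is headed as the safety one). It also causes insurance ("Preferred language' -> Insurance"), but it has no arrow into the exposure. Long-term care and arrival mode are not in this graph.
- **Marking.** In the safety code, insurance is flagged as adjusted ("Insurance [adjusted,pos='-0.343,-0.344") and language is not ("Preferred language' [pos='-0.383,-0.972").
- **Safety covariate list.** Age, sex, Elixhauser score, insurance, temperature, systolic pressure and acute physiology score (APS). The sentence introducing the list refers to primary and secondary outcomes, but the heading and the Figure 3 legend show that it is the safety list. The legend adds that "red variables indicate potential confounders not required for the minimal adjustment set".

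The Data analysis section sets the general rule. Models adjust for factors plausibly linked to the outcome and to treatment hospital, study period or activation. Its fallback propensity weights include language and insurance in every cohort, and add ambulance arrival and long-term care for sepsis cohorts.

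**The concern.** In a given set of patients, what determines who arrives at which ED, and when, does not depend on the outcome analysed later. Two graphs for one exposure node should therefore agree on its causes, or say why they differ. Here each omits causes that the other includes, without comment.

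This matters because the safety list is justified by the safety graph. If that graph leaves out causes of exposure that the SAP states elsewhere, the claim that the omitted variables are not needed has lost its support. Language is the clearest case: one graph makes it a cause of the exposure, and the other makes it a cause of the safety outcome.

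At stake are the comparisons meant to show whether faster antibiotics brought more treatment or more harm. The protocol's aim includes not increasing overtreatment, and its Study Procedures section ties continuation of the programme to benefit and risk.

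**Working it through.** The point is structural. The plan gives no figure to reproduce, and sample size does not enter. The inputs are the arrows in the two Appendix graphs and the two covariate lists.

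**Step 1. Causes of the exposure, side by side.**

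| Cause of exposure | Primary graph | Safety graph | In primary list | In safety list |
|---|---|---|---|---|
| Age, sex, Elixhauser | yes | yes | yes | yes |
| ED arrival mode | yes | not in graph | yes | no |
| Long-term care | yes | not in graph | yes | no |
| Preferred language | yes | in graph, no arrow to exposure | yes | no |
| Insurance | not in graph | yes | no | yes |

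**Step 2. Each graph with its own list.** Every back-door path starts at a cause of the exposure, so adjusting for all of those causes blocks every such path. Each list contains all the causes that its own graph draws. Open back-door paths: 0 in the primary graph and 0 in the safety graph. In the safety graph, the route `exposure <- insurance <- language -> outcome` is closed by insurance. Language is the only unadjusted observed variable lying upstream of both exposure and outcome there, so the legend's statement fits it and is right within that graph.

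**Step 3. Safety graph plus one arrow from the primary graph.** Adding language -> exposure leaves exactly 1 open path with the safety list: `exposure <- language -> safety outcome`. Adjusting for language returns the count to 0.

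**Step 4. Both graphs pooled, with the safety outcome as outcome.** The primary graph's arrows into door-to-antibiotic time are left out.

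| Adjustment set | Open paths | First step back from exposure |
|---|---|---|
| Safety list | 38 | arrival mode 25, long-term care 12, language 1 |
| + language | 36 | arrival mode 24, long-term care 12 |
| + language, arrival mode, long-term care | 0 | none |

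The 36 remaining paths exist because APS is adjusted and is a common effect of illness severity and several unadjusted vital signs and laboratory values. An example is `exposure <- arrival mode <- illness severity -> APS <- O2 saturation -> outcome`. The counts describe structure only and do not measure bias.

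**Step 5. Where a difference in cohort could explain the mismatch.** The primary graph serves the sepsis cohort. Four safety outcomes are also measured there, some after small further exclusions: antibiotic adverse effects, new *C. difficile*, false-positive infection diagnosis and antibiotic spectrum. For these the population and exposure match the primary analysis, yet language, long-term care and arrival mode are dropped. The fallback weights use all three for sepsis cohorts. For the all-ED, high-risk and mimic cohorts, the fallback list keeps language but not the other two.

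**Step 6. Whether the fallback closes the gap.** The weights are used only if the parallel-trends pre-test fails, and the SAP notes that this test looks only at the pre-implementation phase. A shift in patient mix after implementation would not trigger it.

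**The case against.** The strongest reply is that no SAP graph contains the open path. The safety list includes every cause of exposure in the graph that governs it, so it meets the back-door criterion there. That stands. A reader might infer that the safety set fails on the SAP's own arrows, but this is true only of arrows combined from two graphs.

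A second reply is that the safety set also serves broader cohorts, where a shorter list may be deliberate. The fallback weights treat ambulance arrival and long-term care as sepsis-specific, and the Missing data section expects gaps in the all-ED and mimic covariates. This stands for those two variables in those cohorts. It does not explain the sepsis-cohort outcomes, nor the omission of language, which the weights use in every cohort.

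Third, difference-in-differences removes stable differences between sites, and the safety results are hypothesis generating. Both are true, and both limit the consequence. The post-implementation year runs from February 2020 to February 2021, and the SAP puts SARS-CoV-2 test result in its weights. Changing case mix is therefore a reasonable worry, though nothing in the documents shows a differential change in these three factors.

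Two further readings are tempting and unsupported. One is a numerical bias, for instance from a shift in ambulance arrivals: the documents give no risk difference by arrival mode and no differential shift in its share, and neither graph draws an arrow from arrival mode to a safety outcome. The other is that the primary model must add insurance. The primary graph has no insurance node and no open path, so a gap there would need the extra assumption that insurance affects door-to-antibiotic time.

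**Conclusion.** The inconsistency is real, and a modest correction is warranted. One exposure node has six causes in one graph and four in the other, with only age, sex and Elixhauser score in common. The safety list is sufficient under the safety graph and stops being sufficient once the primary graph's causes are accepted. The case is firmest for language, which meets the SAP's own adjustment rule: the primary graph links it to exposure and the safety graph links it to the outcome. For long-term care and arrival mode it rests on the pooled graph and on their use for the same patients elsewhere in the SAP, so it applies to the sepsis-cohort safety outcomes.

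No size can be given. To a first approximation, on a risk-difference scale, bias is the adjusted outcome difference by factor times the differential change in that factor's share between sites. The documents supply neither term, and the bias is zero if the mix moves in parallel. The primary analysis is unaffected.

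**What to change.** 1. Reconcile the two graphs into one set of exposure causes. If a cause is meant to apply only in some cohorts, say so and why.
2. Add `english_preferred_yn` to the safety covariates for all cohorts, matching the fallback weights.
3. Add `snf` and `arrival_mode` for the four sepsis-cohort safety outcomes.
4. Revise the Figure 3 legend and the safety graph code to match.
5. Leave the primary and secondary covariate list as it is.

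All three variables are already named and used in the SAP, so no new data collection is needed. The cost is an edit to the SAP, a few more parameters in models for rare safety outcomes, and possibly some missing language data in the all-ED cohort, which the planned multiple imputation rules can handle.

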#### Heterogeneity of treatment effect for primary outcome

Potential heterogeneity of treatment effect (HTE) will be evaluated using a differences-in-differences-indifferences approach adding interaction terms for subgroups versus study phase and versus control/intervention ED, and a three-way interaction between subgroup, study phase, and control/intervention ED. Subgroup results will be considered descriptive and will be referenced to the overall treatment effect from the primary analysis. The subgroup analyses are not confirmatory, hence no corrections for multiple comparisons will be made.

The following are predefined subgroups for HTE analyses:

- Age (<65 years vs ≥65 years)
- Sex (male vs female)
- Presence of hypotension on ED arrival (SBP <90 or MAP <65)
- Arrival to hospital via ambulance
- Source of infection
- APS quartiles

We will use the following DID formula for HTE analyses:

$$Y_{igts} = \beta_0 + \beta_1 Int_g + \beta_2 Post_t + \beta_3 Sub_s + \beta_4 (Int_g * Post_t) + \beta_5 (Post_t * Sub_s) + \beta_6 (Post_t * Int_g * Sub_s) + \beta_7 Cov$$

Where  $Y_{igts}$  is the door-to-antibiotic time for patient *i* treated at an intervention of non-intervention ED *g* at pre- or post-intervention time *t* from the cohort subgroup *s*. *Int* is a binary indicator for the subject being treated at an intervention hospital; *Post* is a binary indicator the post-intervention period; *Sub* is a binary indicator (or group indicator in the case of APS quartiles) of the subgroup; and *Cov* represents a vector of hospital- and patient-level covariates. The  $\beta_6$  parameter from the regression model presented above estimates the effect measure modification for door-to-antibiotic time in pre-specified subgroups. We will consider the Code Sepsis intervention to have had an impact on the subgroup if  $\beta_6$  is statistically significant and different from zero.

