limited in that it only considers the control and treated groups during the pre-implementation phase. If the pre-test of parallel trends assumption fails, then we will weight the gamma regression model with propensity scores. As demonstrated by Stuart *et. al*, this will balance the covariates amongst the four study groups defined by their treatment status as well as time (pre vs post). We will leverage the covariate balancing propensity score (CBPS) library in R to generate propensity scores. This weighting approach can recover treatment effects in that it allows for adjustments due to observed baseline covariates that differ either across groups or over time. Covariates that will be used in generating propensity scores will include age; sex; weighted Elixhauser comorbidity score; English language preference; first-available heart rate, temperature, systolic blood pressure, and respiratory rate; acute physiology score; ED arrival at nightime (10 pm to 6:59 am), ED arrival on weekend (midnight Saturday to 11:59 pm Sunday), SARS-CoV-2 test result (positive, negative, or not performed during ED-associated hospitalization or within 14 days preceding ED arrival); and insurance type. For analyses involving a cohort of patients with sepsis, propensity score covariates will additionally include arrival to ED via ambulance; presentation from a long term care facility; serum lactic acid level checked and ≥2 mmol/dL; ED SOFA score; and ED-diagnosed infection source.

In order to account for the right skew known to exist in door-to-antibiotic time we will use generalized linear gamma regression to estimate the DID. Evaluation of secondary outcomes will employ an analogous approach using multivariable linear, Poisson, logistic, or gamma regression as appropriate. Data from the wash-in phase will be excluded from DID analyses. All multivariable models will be adjusted for demographic and clinical parameters with known or plausible associations with both outcomes and treatment hospital, presentation before or after Code Sepsis implementation, and/or Code Sepsis activation as well as select precision variables as detailed below. Analyses for secondary, safety, and heterogeneity of treatment effect outcomes will not be adjusted for multiple comparisons and will therefore be considered hypothesis generating.

Statistical significance will be set to p < 0.05. All analyses will be conducted with R.

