#### Primary and secondary outcome analysis covariates

Variables listed below will be included in multivariable adjusted analyses for primary and secondary outcomes listed above. Variables are also included in any associated subgroup and sensitivity analyses for these outcomes. For heterogeneity of treatment effect analyses, where continuous variables are categorized or dichotomized, the corresponding adjustment variable will also be categorized analogously in the adjustment model and for creation of the interaction term.

- Age (age, continuous)
- Female sex (sex, binary)
- Presentation from a long-term care facility (snf, binary)
- Weighted Elixhauser comorbidity score (elixhauser\_vw, continuous)
- Arrival to ED via ambulance (arrival\_mode, binary)
- English is preferred language (english\_preferred\_yn, binary)
- First-available temperature in ED (vs\_temp\_cat, categorical, reference group = 1 [temp 36-38°C])
- First-available systolic blood pressure in ED (**vs\_sbp**, continuous)
- Acute physiology score (aps\_24h, continuous)
- ED SOFA score (**sofa\_ed**, continuous)

• ED-diagnosed infection source (**source\_ed\_final\_simpler**, categorical, reference group = 1 [pneumonia])

**Figure 2.** Adjustment variables for primary & secondary multivariable analyses. The primary exposure is intervention ED arrival post-intervention and the primary outcome is door-to-antibiotic time. White symbols indicate potential confounders or precision variables included in the multivariable model, gray symbols represent an unobserved variable, and blue symbols (other than the outcome) represent an ancestor of outcome not included in the multivariable model.

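### The printed subgroup (HTE) equation leaves out the subgroup-by-site interaction that the SAP text names, so β6 as printed measures effect modification only if the baseline site-by-subgroup gap is zero

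*SAP*

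**What the plan says.** All of this is in the SAP, mostly under Heterogeneity of treatment effect for primary outcome.

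- The text says the model adds "interaction terms for subgroups versus study phase and versus control/intervention ED, and a three-way interaction between subgroup, study phase, and control/intervention ED".
- The equation is introduced with "We will use the following DID formula for HTE analyses". After the intercept and the main effects of site, period and subgroup it reads "\beta_4 (Int_g * Post_t) + \beta_5 (Post_t * Sub_s) + \beta_6 (Post_t * Int_g * Sub_s) + \beta_7 Cov". The products are Int×Post, Post×Sub and Post×Int×Sub. Int×Sub is absent.
- On β6, the SAP says that this "parameter from the regression model presented above estimates the effect measure modification for door-to-antibiotic time in pre-specified subgroups".
- The decision rule is "We will consider the Code Sepsis intervention to have had an impact on the subgroup if" β6 differs significantly from zero.
- On status: "Subgroup results will be considered descriptive and will be referenced to the overall treatment effect from the primary analysis". The Data analysis section also treats these results as hypothesis generating.
- The covariate list (Primary and secondary outcome analysis covariates) holds main effects only. Its one rule for these analyses is that, where a continuous variable is cut into groups, "the corresponding adjustment variable will also be categorized analogously in the adjustment model and for creation of the interaction term". That recodes a covariate and does not supply Int×Sub.

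**The concern.** The text and the equation specify different models. This does not look like a PDF artefact: the coefficients run from β0 to β7 without a gap, each product has its own coefficient, and the text cites β6 as the three-way term.

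A triple difference subtracts the pre-period site-by-subgroup contrast from the post-period one. Int×Sub is the term that carries the pre-period contrast. Without it, a difference that existed before Code Sepsis is credited to Code Sepsis. An example would be an intervention ED that already handled ambulance arrivals differently from the control EDs.

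A zero gap cannot be taken for granted. Protocol section 4.1 sets a tertiary teaching ED against two regional referral EDs staffed by other physician groups. Protocol section 3.1 reports five-fold variation between physicians in median door-to-antibiotic time. What is at stake is a wrong subgroup statement reached by following the SAP's own rule.

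**Working it through.** **Inputs.** From the SAP's Power section: 1,650 intervention and 2,200 control sepsis patients per year (each analysis phase is one year), mean 170 and SD 75 minutes. Significance is p < 0.05, taken as two-sided. D and the subgroup shares are not in the documents, so the values below are assumed for illustration. The linear figures use no covariates and a normal approximation. The SAP states no figure for this analysis, so there is none to reproduce.

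**Step 1: what β6 estimates.** There are eight cells (site × phase × subgroup). In the printed model β2, β4, β5 and β6 appear only after implementation, so they fit the four post-period cells freely. Hence

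`β6 = post-period site-by-subgroup contrast = true modification + D`.

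Weighted least-squares projection on the cell means gives a bias of 1.00 D at equal shares of 50%, 30% and 15%, and also with unequal shares (20% control, 40% intervention). With Int×Sub added the bias is 0. If the true modification is −10 minutes, D = +10 gives β6 = 0 (effect hidden) and D = +20 gives β6 = +10 (sign reversed).

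**Step 2: standard error and false rejection.** As printed,

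`SE(β6) = 75 × √(sum of 1/n over the four post-period cells)`.

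At a 50% share: 75 × √(2/825 + 2/1,100) = 4.89. With Int×Sub the four pre-period cells enter as well, so the SE is √2 times larger, 6.91. The chance of rejecting when there is no true modification is `Φ(D/SE − 1.96) + Φ(−D/SE − 1.96)`. At D = 10, D/SE = 2.05 and the chance is 53%.

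| Share | SE as printed | SE with Int×Sub | Rejection at D = 2 / 5 / 10 min | D at which rejection is 10% |
|---|---|---|---|---|
| 50% | 4.89 | 6.91 | 7% / 18% / 53% | 3.2 |
| 30% | 5.33 | 7.54 | 7% / 16% / 47% | 3.5 |
| 15% | 6.84 | 9.67 | 6% / 11% / 31% | 4.5 |

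With Int×Sub, rejection is 5% at every D.

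**Step 3: the subgroup-specific effects.** The additive pre-period fit pushes part of D into the site term, so β4 (the reference-subgroup effect) shifts by −share × D: −0.50 D, −0.30 D and −0.15 D. The named subgroup's effect, β4 + β6, shifts by (1 − share) × D. With unequal shares the weight on each subgroup is n_c·n_i/(n_c + n_i). That is 440 × 660/1,100 = 264 for the named subgroup and 1,760 × 990/2,750 = 633.6 for the reference, so β4 shifts by −264/897.6 = −0.294 D.

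**Step 4: APS quartiles.** With 25% in each quartile and a gap only in the top one, that level's coefficient is falsely significant 11% and 30% of the time at D = 5 and 10. A joint 3-df test gives 10% and 29%.

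**Step 5: gamma model.** The SAP plans gamma regression and does not state the link. A log-link simulation (shape (170/75)², 4,000 runs per setting) at a 50% share gives 18% and 50% at D = 5 and 10. At D = 10 the β6 ratio is 1.06 (180/170) when it should be 1.00. With Int×Sub, rejection is 4.6–5.3% at every D tried.

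**The case against.** The best defence is that the right analysis is already written down. The section describes a triple difference, names the subgroup-by-site term and reads β6 as effect modification; only the displayed line departs from that. The SAP also states "All analyses will be conducted with R", and an R formula `Post*Int*Sub` brings in Int:Sub automatically. Protocol section 7.2 plans analyses stratified by sex and by hypotension on arrival, and a separate difference-in-differences in each stratum has its own site term, so it cannot carry this bias. D is unknown, must be what remains after covariate adjustment, and does little harm at 2 minutes or less. The results are descriptive.

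Much of this stands. The omission is most likely a dropped term, and harm requires both literal coding and a material D. But the SAP does not say that the text overrides the equation, so two careful analysts could follow it and report different subgroup answers. The stratified analyses cover two of the SAP's six subgroups and support restoring the term. A descriptive estimate must still estimate what it claims to, and the SAP attaches a significance rule to this one.

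**Conclusion.** The concern holds. The text and the equation disagree, and as printed β6 equals effect modification plus the baseline site-by-subgroup gap on the link scale. That result is algebraic and needs no assumed value for D.

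The practical size does depend on D. At 2 minutes or less, false rejection stays near nominal (6–7%). At 10 minutes it is 31–53% for two-level subgroups with shares of 15–50%. These rates rest on the SAP's planning counts and SD, no covariates and no true modification, and they show possible harm, not expected harm. The problem is confined to the subgroup analyses. It should be corrected, but it does not threaten the trial's main conclusions.

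**What to change.** Add Int_g × Sub_s, with its own coefficient, to the printed equation and to the code, using all levels for infection source and APS quartiles. Renumber the coefficients so that the interpretation and the decision rule point to the three-way term. Keep the results descriptive, as the SAP has them.

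The cost is one term and some precision. The SE of the three-way coefficient rises by a factor of 1.41 (two-level values in the table above; APS quartile coefficients from 6.91 to 9.77 minutes). SEs of subgroup-specific effects rise less. At shares of 50%, 30% and 15% the factors are 1.15, 1.08 and 1.04 for the reference subgroup, and 1.15, 1.24 and 1.32 for the named subgroup. The primary, secondary and safety analyses do not change.

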#### 7.2 Multivariable models

Multivariable models will be adjusted for demographic and clinical parameters with known or plausible associations with both door-to-antibiotic time and treatment hospital, presentation before or after Code Sepsis implementation, and/or Code Sepsis activation. Evaluation of secondary outcomes will employ an analogous approach using multivariable linear, Poisson, or logistic regression as appropriate. Repeating the quasi-experimental analysis for the primary and key secondary outcomes after stratification (rather than adjustment) by (1) sex and (2) hypotension present versus absent on ED arrival will allow evaluation of whether these patient characteristics modify the effects of Code Sepsis implementation. In order to measure how the Code Sepsis protocol influences the care of its core target population, we will perform analyses comparing selected outcomes among the subset of patients who have ED triage data suggesting a strong possibility of sepsis. Outcomes to be evaluated in the sensitivity analyses will include door-to-antibiotic time, antibiotic treatment fraction, and antibiotic treatment spectrum.

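### The subgroup rule uses the interaction coefficient β6 to declare an impact within a subgroup, but β6 measures only how the effect differs between subgroup levels

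*SAP*

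**What the plan says.** The SAP section on heterogeneity of treatment effect for the primary outcome names six subgroup factors: age, sex, hypotension on arrival, ambulance arrival, infection source and APS quartile. It describes the model as "adding interaction terms for subgroups versus study phase and versus control/intervention ED", plus a three-way interaction. The printed equation contains phase-by-subgroup and the three-way term "Post_t * Int_g * Sub_s", whose coefficient is β6. It contains no hospital-by-subgroup term.

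The text says, correctly, that β6 "estimates the effect measure modification for door-to-antibiotic time in pre-specified subgroups". The next sentence sets the decision rule: "We will consider the Code Sepsis intervention to have had an impact on the subgroup if" β6 is statistically significant and different from zero. No test or interval is specified for the effect within a level.

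On the standing of these results the section says: "Subgroup results will be considered descriptive and will be referenced to the overall treatment effect from the primary analysis", and "The subgroup analyses are not confirmatory, hence no corrections for multiple comparisons will be made". The SAP's Data analysis section also treats heterogeneity results as hypothesis generating.

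Protocol section 7.2 plans to repeat the quasi-experimental analysis "after stratification (rather than adjustment) by (1) sex and (2) hypotension present versus absent on ED arrival". The SAP does not repeat this.

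**The concern.** The two consecutive sentences about β6 do not fit together. The first says that it measures a difference between levels. The second uses its significance to conclude that the intervention worked in a level. The SAP uses almost the same sentence for β3 in its Data analysis section and for β4 in the interrupted time series. It is valid in both places, because those coefficients are the intervention effect. Here it is attached to an interaction.

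What is at stake is the reported subgroup findings. An equal benefit in both levels would usually trigger no declaration, and a level with no benefit could be reported as having been affected.

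**Working it through.** **What the coefficients mean.** Code the subgroup as s = 0 (reference) or s = 1. In the printed equation the pre-to-post change at the intervention ED is β2 + β4 + (β5 + β6)s. At the control EDs it is β2 + β5·s. The difference-in-differences is therefore β4 + β6·s, that is, β4 in the reference level and β4+β6 in the other. Adding a hospital-by-subgroup term does not change this, because that term cancels in the pre-to-post change. Recoding which level is the reference changes the sign of β6 but not its p-value, so for a two-level factor the rule gives the same answer for both levels.

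**Inputs.** From the SAP's Power section: 1,650 intervention and 2,200 control sepsis patients per year, SD 75 minutes, and 90% power for a 16-minute difference-in-differences. From the Data analysis section: p < 0.05, taken here as two-sided. Assumptions: independent patients, a linear scale in minutes, and a subgroup share p of 50%, 30% or 20%, since the documents give none.

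**The plan's own figure.** SE(DID) = 75·√(2/1650 + 2/2200) = 3.45 minutes. Power at 16 minutes is Φ(16/3.45 − 1.96) = 99.6%, so the stated 90% is not reproduced from the printed inputs. It came from a simulation whose details are not in the documents, and the gap is in the conservative direction. The stated power implies SE = 16/(1.960 + 1.282) = 4.94 minutes. Both SEs are carried forward.

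**Formulas, with hospital-by-subgroup in the model.** SE(β4+β6) = SE(DID)/√p. SE(β6) = SE(DID)/√(p(1−p)). At p = 50% and SE 3.45 these are 4.89 and 6.91 minutes. The chance of rejection for a true value d is approximately Φ(|d|/SE − 1.96).

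*Scenario A: 16-minute benefit in both levels.* Here β6 = 0, so the rule declares impact 5% of the time, and would do so for any size of uniform benefit.

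*Scenario B: 16 minutes in the reference level, zero in the subgroup.* Here β6 = +16 minutes. A direct test of β4+β6 would reject 5% of the time.

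| SE(DID) | Share p | SE(β4+β6) | SE(β6) | A: direct test | A: SAP rule | B: SAP rule (false) |
|---|---|---|---|---|---|---|
| 3.45 | 50% | 4.89 | 6.91 | 91% | 5% | 64% |
| 3.45 | 30% | 6.31 | 7.54 | 72% | 5% | 57% |
| 3.45 | 20% | 7.72 | 8.64 | 54% | 5% | 46% |
| 4.94 | 50% | 6.98 | 9.87 | 63% | 5% | 37% |
| 4.94 | 30% | 9.01 | 10.77 | 43% | 5% | 32% |
| 4.94 | 20% | 11.04 | 12.34 | 31% | 5% | 25% |

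**Simulation check (p = 50%, SD 75).** Linear model, 1,000 runs per scenario: in A the rule fired in 5.8% and the direct test in 90%; in B they fired in 62% and 5%. With a uniform 36-minute benefit the rule fired in 4.0% and the direct test in 100%. In a gamma model with log link (300 runs, uniform 16-minute benefit) the rule fired in 4% and the direct test in 91%.

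**The equation exactly as printed (p = 50%).** Without hospital-by-subgroup, β6 is estimated from the post period alone: SE(β6) = 75·√(2/825 + 2/1100) = 4.89. SE(β4+β6) = 75·√(1/825 + 1/1100 + 1/1650 + 1/2200) = 4.23, which gives the direct test 97% power at 16 minutes. This precision is bought by assuming no baseline hospital-by-subgroup difference. If that difference were 10 or 20 minutes (assumed) with no intervention effect anywhere, β6 would absorb it, and the rule would fire with probability Φ(10/4.89 − 1.96) = 53% or Φ(20/4.89 − 1.96) = 98%. With the term included the rate returns to about 5%.

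**The case against.** The defence rests on context. The section concerns heterogeneity, the preceding sentence defines β6 properly, and the results are descriptive, unadjusted and read against the overall effect. No primary, secondary or safety conclusion depends on β6. All of this stands and limits the harm. It does not change which quantity the rule tests, and reference to the overall effect does not supply an effect for a level.

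A reader might infer that the SAP would declare a uniform benefit absent. It does not: it says what a significant β6 means and attaches no conclusion to a non-significant one. The failure in that direction is a missing declaration. The false declaration in scenario B is not answered by this reply.

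A reader might also infer that infection source and APS quartiles would be tested one level at a time. The SAP refers to a single β6 and is silent on how several such terms are tested. That is a gap, not a plan for separate tests.

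The stratified analyses in protocol section 7.2 would give level-specific effects for sex and hypotension. This is a fair point for those two factors. It leaves age, ambulance arrival, infection source and APS quartile uncovered, and the SAP neither repeats it nor adjusts its rule.

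Finally, the size depends on assumption. More extreme patterns give larger figures: 32 minutes against zero at a 50% share gives 99.6%, or 90% with the implied SE. Nothing in the documents makes that pattern the expected one.

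**Conclusion.** The rule is wrong as written. β6 answers whether the effect differs between levels; it cannot show whether there is an effect in a level. The 5% firing rate under uniform benefit follows from the algebra once the model includes hospital-by-subgroup or there is no baseline difference of that kind. The other percentages are illustrations that rest on the stated assumptions. The SAP specifies gamma regression without naming a link. Under a log link β6 is a ratio of ratios and a uniform effect means a uniform percentage change, but the same fault remains.

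The consequence is limited to descriptive, hypothesis-generating subgroup statements. The documents do not support the stronger reading that the trial's main conclusion is affected. This should be fixed before results are reported, as a correction of wording and model specification.

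**What to change.** Make two changes in the SAP's heterogeneity section, together:

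1. Add the hospital-by-subgroup term to the printed equation, as the text already promises. Without it, β4 and β4+β6 are clean level-specific effects only if there is no baseline hospital-by-subgroup difference.

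2. Replace the last sentence with: *β6 (a joint test across levels for infection source and APS quartiles) assesses whether the effect differs between subgroups. The effect in each level is reported as β4 (reference) or β4+β6 (other levels), on the scale of the fitted model, with 95% CIs. No claim of impact within a subgroup is based on β6.*

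The cost is one model term, one sentence, one linear contrast per non-reference level and a joint test for the two multi-level factors. No new data are needed. Intervals from the full model will be wider than those from the printed one (at a 50% share, SE of β4+β6 4.89 against 4.23 minutes).
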